	Gadoteric Acid Meglumine Salt: Patients who have undergone contrast-enhanced MRI using Gadoteric Acid Meglumine Salt contrast agent for clinical purposes.	Drug: Gadoteric Acid Meglumine Salt Injection (Jia Di Xian™)
Eligibility Criteria	
Inclusion Criteria:
 
 1. Patients aged 18 to 80 years old who require gadolinium-based CE-MRI; 2. Patients with renal function $30\text{ml/min}/1.73\text{m}^2 \leq \text{eGFR} < 90\text{ml/min}/1.73\text{m}^2$; 3. Patients who are able and willing to comply with the required inspection requirements. 
Exclusion Criteria:
 
 1. Patient who experienced allergic reactions to previous gadolinium based contrast agents; 	

	
 2. Patient who had used gadolinium based contrast agents within 3 months; 3. Patient with acute renal failure; 4. Patient who cannot comply with or cannot tolerate the necessary fluid replenishment procedures; 5. Patient with major mental illness, impaired consciousness or other diseases considered by researchers to affect observation.
Outcome Measure	
Primary Outcome indicators: Record the incidence of various adverse events;
 
Secondary outcome indicators:
 
 1. Changes of serum creatinine and inflammatory factors (TNF-α, hs-CRP, IL-6) before and after CE-MRI 2. Patient skin examination and evaluation: evaluation of relevant indicators of skin biopsy (proliferation of fibroblasts in subcutaneous tissue, thickening of collagen fiber bundles)
Enrollment	600 participants

I. Sponsor Information

(I) Name of sponsor

[name]

(II) Address of sponsor

Lishui Central Hospital, [name]

(III) Contact information of sponsor

[name]

(IV) Relevant qualification documents of sponsor

The relevant qualification documents of the sponsor will be provided in a separate letter.

II. Purpose and contents of clinical trial

(I) Purpose

To compare the incidence of adverse events of linear and macrocyclic gadolinium-based contrast agents for patients with mild to moderate renal insufficiency undergoing enhanced magnetic resonance imaging.

(II) Contents

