This trial is a prospective, interventional study. According to the requirements of the study, 600 cases of patients with mild to moderate renal insufficiency were enrolled. Gadodiamide and gadoteric acid meglumine salt were used for enhanced MRI. Observe the adverse reactions within 60 minutes of using the gadolinium contrast agents; follow up by telephone at 3, 6, 12, and 24 months after the inspection.

III. Background information of clinical trials

The principle of Magnetic Resonance Imaging (MRI) relies on the magnetic field generated by water molecules in the human body. It has high resolution in soft tissues (such as the nervous system, parenchymal organs, and muscle tissue), and uses non-ionizing electromagnetic radiation. Known exposure risk, many imaging parameters (sequence, proton density, T1 and T2 relaxation time) and many other advantages, since it entered the clinic in the 1980s, it has been clinically proven to be a valuable imaging diagnostic method. In the early clinical practice, MRI was mainly used for unenhanced magnetic resonance imaging, and the value of Contrast Enhanced-Magnetic Resonance Imaging (CE-MRI) in the diagnosis of diseases was not recognized. In the later stage, due to CE-MRI in small lesions, inflammation, edema and tumor Such diagnostic advantages have become an important supplement to MRI. At least about 30% of disease MRI diagnosis requires injection of magnetic resonance contrast agents.

In 2000, Cowper described the mucoedema-like sclerosis skin disease of renal dialysis patients in the Lancet magazine, that is, Nephrogenic Systemic Fibrosis (NSF). In 2006, Grobner

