deposition disease, GDD) harm or potential harm to the human body, the FDA banned some linear GBCAs (such as: gadolinium diamine, gadolinium meglumine) in July 2015) Is used for special populations (eGFR<30ml/min/1.73m², acute kidney injury), while the European Medicines Agency (EMA) banned some linear GBCA intravenous (such as: gadolinium diamine, Gadopentetate meglumine) is used for body enhancement. Because the stability of large ring GBCA is better than linear GBCA, FDA and EMA do not make special requirements. Gd-terol, gadobutrol and meglumine gadoterate are all macrocyclic GBCA. Gd-DOTA is the only ionic macrocyclic gadolinium contrast agent with the best stability (conditional stability constant, dissociation half-life and chelation Evaluation of parameters such as residues), the safety is better. At present, the GBCA approved by the China Food and Drug Administration (CFDA) includes gadopentetate meglumine, gadolinium diamine, gadolinium fuseamide, gadolinium benzamide, gadolinium disodium gadolinate, and gadolinium. Butrol, gadoterol and gadoterate meglumine. In this study, linear gadolinium and macrocyclic gadolinium were used in enhanced magnetic resonance examinations. Acute adverse reactions (1h) and delayed adverse reactions (1h-1W) in patients with mild to moderate renal insufficiency after contrast injection , The occurrence of late-onset adverse reactions (1W-3M). To explore the incidence of adverse reactions of linear gadolinium contrast agents represented by gadolinium bisamine and macrocyclic gadolinium contrast agents represented by gadolinium meglumine in patients with mild to moderate renal insufficiency. For patients with mild to moderate renal insufficiency when doing CE-MRI, make the best choice of gadolinium to reduce the incidence of adverse reactions in such patients during enhanced MRI.

IV. The characteristics and safety of the drug

(I) Characteristics of the drug

Generic name: Gadodiamide Injection

Product name: OMNISCAN

Sample specifications: 15ml: 4.305g (a sterile solution containing 287mg/ml gadodiamide)

Generic name: Gadoteric Acid Meglumine Salt Injection

Commodity name: Jia Di Xian

Sample specifications: 15ml: 5.654g (a sterile solution containing 377mg/ml gadoteric acid meglumine salt)

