Visit 4: within 6 months after contrast injection;

Visit 5: within 12 months after contrast injection;

Visit 6: within 24 months after contrast injection;

Visit content: study-CRF table-patient basic information table

Visit 1: study-CRF table-patient basic information table

1. Name of hospital:
2. Registration Date:
3. Contact details of the patient/its agent:
4. source: Outpatient () Hospitalized ();
5. Clinical department;
6. Name:
7. Sex: Male () Female ();
8. Age:
9. Weight: Kg;
10. Height: CM;
11. CE-MRI informed: yes () no ();
12. CE-MRI Indications:

13. Gadolinium contrast injection time:

14. Gadolinium contrast agent injection volume: ml;

15. Gadolinium contrast injection method: Push () Machine injection () (Please mark the injection speed);

16. Previous image enhancement examination history: time; Contrast agent name; Yes/No adverse events occurred;

a) yes time symptom severity;

17. Past history of adverse drug reactions: yes/no, yes time、AE symptom、severity;

18. The latest serological examination before CE-MRI and the serological examination within 2 weeks after CE-MRI;

19. History of allergy: yes/no, yes, allergy description;

20. Suspected existing disease:

21. Existing disease treatment plan: medical treatment () oral () Intramuscular injection () Intravenous injection () Surgical treatment () surgical intervention () Else;

22. History of illness:

a) Disease name Date of diagnosis duration;

23. Daily medication (Take medication within 1 week):

a) Generic name of the drug Taking method dose

24. Other information

25. Adverse event: yes () no ()

Visit 2, Visit 3, Visit 4, Visit 5 and Visit 6 Study-CRF Form-Contrast Adverse Events

1. Name:
2. Sex:
3. Age:
4. Weight:
5. Time to onset of adverse events:
6. Severity assessment:
7. Suspected drugs: Generic name (including dosage form)、Manufacturer、Production batch、Dosage、Start and end time of medication、Reason for medication;

8. Concomitant drugs: Generic name (including dosage form)、Manufacturer、Production batch、
Dosage、Start and end time of medication、Reason for medication

Concomitant drugs are those used within 24 hours;

9. Other suspected factors: Such as: patient disease progression, patient treatment plan, etc.;

10. Adverse events affect organ systems:

11. Adverse event name: refer to MedADR glossary;

12. Process description and handling of adverse events (attachment available);

13. Adverse event results:

Recover () Improve () Not getting better () Unclear ()

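### Late adverse events are sought by telephone with no standard question and no masking of the caller described, so unequal questioning could make the all-cause event count differ between the two agents

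*Combined protocol and SAP*

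**What the plan says.** The Protocol Summary gives the primary outcome as "Record the incidence of various adverse events". Section II (I) makes the aim a comparison of that incidence between the two agents. Section VI (IV) defines an adverse event without requiring a causal link to the drug.

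Events are sought once in the hour after injection (Visit 2). After that, section II (II) says: "follow up by telephone at 3, 6, 12, and 24 months after the inspection". These calls are Visits 3-6 in section VI (III).

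One form serves all five contacts: "Visit 2, Visit 3, Visit 4, Visit 5 and Visit 6 Study-CRF Form-Contrast Adverse Events". Its item 7 reads "Suspected drugs: Generic name (including dosage form)、Manufacturer、Production batch、Dosage、Start and end time of medication、Reason for medication", and its item 11 reads "Adverse event name: refer to MedADR glossary". It has no list of symptoms to ask about, no opening question and no box for a patient without an event. The field "Adverse event: yes () no" is item 25 of the Visit 1 form only.

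No section describes masking of patient, caller or assessor. Section IX (I) names a blind review once, in a general list of data management steps. Section IX (I) also mentions guidelines for completing the CRF, which are not supplied.

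Section III states an expectation about the agents: "Gd-DOTA is the only ionic macrocyclic gadolinium contrast agent with the best stability". The same sentence goes on to say that its safety is better.

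**The concern.** Most adverse events at 3 to 24 months will be known only if someone asks and the patient mentions them. If the caller may know the agent, has read that one agent is safer and has no set question, the depth of questioning can vary by agent. That is detection bias in the primary outcome.

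Counting events regardless of cause protects against biased attribution, because nobody has to judge whether the drug was responsible. It does not protect against an event that was never elicited. The exact confidence intervals and logistic regression in section IX (II) work on recorded events and cannot restore missing ones. Because the Visit 2-6 form has no field for a negative answer, unequal questioning would also leave no trace in its data. At stake is whether a difference between the agents, or its absence, reflects the agents or the calls.

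**Working it through.** **Documents side by side**

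1. Contacts after injection: Visits 2, 3, 4, 5 and 6. Telephone contacts: 3, 4, 5 and 6. So 4 of 5 are calls.
2. Standard question: none in section VI (III). Item 11 points to a glossary for naming an event already found.
3. Negative answer: none on the Visit 2-6 form.
4. Masking of the caller: none described.
5. Stated expectation: section III favours the macrocyclic agent.

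Together these permit unequal elicitation. They do not show that it will happen.

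**The plan's own figure**

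Section IX (II) gives 600 cases with no power, effect size, event rate or allocation ratio, so the number cannot be reproduced.

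**Illustration of size**

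Inputs:
- n = 300 per agent (assumed equal split of 600).
- Two-sided 5% level (section IX (II)).
- True incidence *p*, equal for both agents. The main case is 8.5%, the all-cause figure for gadoterate trials in section IV (II): 241/2822 = 8.54%. A low case is 4%, matching the possibly related figure there: 113/2822 = 4.0%. A high case of 20% is assumed, since four calls over 24 months may find more.
- Share of events found: 90% with one agent, 80% or 70% with the other (assumed).

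Formulas:
- Observed proportion = *p* × share found.
- Apparent OR = [p1/(1 − p1)] / [p2/(1 − p2)].
- False rejection = exact binomial probability that the pooled two-proportion test gives |z| > 1.96, with z = (p̂1 − p̂2)/√[2p̄(1 − p̄)/n]. This stands in for the planned logistic regression.

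Main case, 90% v 70%:
- p1 = 0.085 × 0.9 = 0.0765; p2 = 0.085 × 0.7 = 0.0595.
- OR = (0.0765/0.9235)/(0.0595/0.9405) = 0.0828/0.0633 = 1.31.
- Approximate check: p̄ = 0.068; SE = √(2 × 0.068 × 0.932/300) = 0.0206; expected z = 0.017/0.0206 = 0.83. The chance of exceeding 1.96 in that direction is about 0.13. The exact two-sided value is 0.133.

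| True incidence | Share found | Observed | Apparent OR | False rejection |
|---|---|---|---|---|
| 8.5% | 90% v 80% | 7.65% v 6.80% | 1.14 | 7.0% |
| 8.5% | 90% v 70% | 7.65% v 5.95% | 1.31 | 13.3% |
| 4% | 90% v 80% | 3.6% v 3.2% | 1.13 | 5.8% |
| 4% | 90% v 70% | 3.6% v 2.8% | 1.30 | 8.5% |
| 20% (assumed) | 90% v 80% | 18% v 16% | 1.15 | 9.9% |
| 20% (assumed) | 90% v 70% | 18% v 14% | 1.35 | 26.6% |

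With equal detection the same test rejects 5.1% of the time at 8.5% and 5.0% at 4% and 20%.

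**The case against.** The strongest reply is that item 7 proves little. It asks about suspected drugs on an event report form, most of whose other items (onset, severity, outcome, rechallenge, relevance) make sense only once an event has been reported. Section VI (IV) allows 15 days to complete the report for a known mild to moderate reaction, so the paperwork may follow the call. A reader might infer from item 7 that the caller has the agent in front of them before asking anything. The documents do not support that. Item 7 shows only that the form is not masked. This part of the objection stands, and the point rests instead on the absence of any described question or masking.

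A reader might also infer that no script or masking exists. That too goes beyond the documents. The protocol refers to SOPs (section VII) and CRF guidelines that are not supplied, and the process figure in section VI (I) is not shown. The correct wording is that none is described. The protocol also does not say who makes the calls; site staff is a natural inference from the single-centre design, no more.

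On size, the detection shares are assumed. The calculation applies the gap to every event, although Visit 2 is not a telephone contact, and deaths and hospitalisations should depend less on probing than mild symptoms do. A higher incidence makes the effect look more dramatic: at 30% the false rejection rates would be 13% and 41%. But no such incidence appears in the documents. At the rates that section IV (II) does give, the inflation is modest.

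None of this answers the main point. The form cannot show whether a patient was asked, and nothing in the plan makes the questioning the same for both agents.

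**Conclusion.** The concern holds as a design weakness that should be corrected. Events at Visits 3-6 depend on telephone questioning for which no standard wording, no recorded negative answer and no masking are described, in a protocol that states which agent it expects to be safer. The all-cause count can therefore differ between agents through questioning alone, and no planned analysis can remove such a difference.

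The documents do not establish its size or direction; a reader should not conclude that the results will favour the macrocyclic agent. If 300 patients per agent have equal true incidence of 8.5% and the detection gap is 10 or 20 percentage points, false rejection rises from 5% to about 7% or 13%. Across true incidences of 4% to 20%, the same gaps give about 6% to 27%. The 8.5% comes from trials of one agent and may not match two years of follow-up in this population.

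**What to change.** Before calls begin:

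1. Write one fixed, agent-neutral symptom list and have it read word for word at every call.
2. Add a yes/no event field to the Visit 2-6 form and complete it for every patient at every contact, so that a negative answer differs from a question not asked.
3. Give the caller a call sheet that does not show the agent.
4. Complete item 7 after the call is closed, from the injection record. The Visit 1 form lists injection time, volume ("Gadolinium contrast agent injection volume: ml") and method but has no field for which study agent was given, so add one and keep it off the call sheet.
5. Where possible, use existing staff who did not give that patient's injection.

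The cost is about one page of script, two added fields and a reordered eCRF, with no extra contacts. Whether item 5 needs more staff cannot be judged, because the documents do not describe staffing for the calls. Masking will be imperfect if a patient knows or volunteers the agent, and masking the caller does not remove differences in the patient's own reporting. If the SOPs or CRF guidelines already contain a script or masking, the protocol should say so.

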Have adverse events () manifestation: _____

death () Direct cause of death: _____ Time of death: y m d

14. Impact on the original disease:

Not obvious () Prolonged course () Worsening () Cause adverse events () Cause death ()

15. Whether the withdrawal/reduction reaction is reduced or disappeared:

yes () no () unclear () No discontinuation or dose reduction ()

Whether the same reaction occurs again after re-use

yes () no () unclear () Unused ()

16. Relevance evaluation:

Certain () Very likely () Possible () May be irrelevant ()

Wait to be evaluated () Can't evaluate ()

17. Reporter's information: name, contact number, email address, occupation

(IV) Evaluation Standard

1. Adverse events

Adverse Event (AE) : Adverse clinical events that occur during the course of drug treatment may not necessarily have a causal relationship with the drug.

Serious Adverse Event (Serious Adverse Event, SAE): the reaction of one of the following

damages caused by the use of drugs:

- 1) Cause death;
- 2) Life threatening;
- 3) Carcinogenic, teratogenic, and birth defects;
- 4) Cause significant or permanent human disability or damage to organ function;
- 5) Lead to hospitalization or prolonged hospital stay;
- 6) Causes other important medical events, if not treated, the conditions listed above may occur.

Report serious adverse events:

- 1) When an aggregated, serious, or new (not listed in the ACR Contrast Media Guide) adverse reaction occurs, the investigator must within 24 hours of being notified:
- 2) Fill in the "Adverse Event/Reaction Report Form" and report to the Research Center Ethics Committee;
- 3) Entering adverse reaction events into EDC allows researchers to process relevant safety information/take corresponding measures immediately;
- 4) When a known mild to moderate adverse reaction occurs, the researcher needs to fill in the "Adverse Event/Reaction Report Form" within 15 days after being notified, and complete the entry of the adverse reaction event into the EDC to facilitate timely information about the adverse event;

2. Severity assessment

AE severity refers to the degree of occurrence of a specific event (which can be SAE or ordinary AE), but the event itself may have relatively small medical significance.

Principle of severity

Mild symptoms or signs that are easily tolerated

Moderate symptoms and signs cause discomfort and affect daily life;

Severe Cannot engage in daily life or work, need sick leave or necessary treatment.

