3. Causality assessment

The causal relationship between adverse events and drugs is often based on the investigator's clinical judgment and understanding of the trial drug, but generally can be comprehensively analyzed from the following aspects:

The time relationship between medication and adverse events and whether there is a

dose-effect relationship;

Whether it is a known type of drug reaction;

Whether the adverse events alleviate or disappear after stopping or reducing the dose;

Under strict and safe conditions, when the test is repeated, whether the adverse event recurs;

Whether adverse events can be explained by the effects of concomitant medications, the patient's disease progression, and the effects of other treatments;

The causal relationship between adverse events and drugs can be judged according to the WHO Uppsala ADR Testing Center Guidelines. The six-level evaluation standard is affirmative, very likely, possible, unlikely, unassessed, unable to assess.

VII. Trial quality control

The quality of clinical trials refers to its scientificity, reliability, accuracy and completeness.

Quality assurance is an important cornerstone of whether the trial can be successful. As a quality management standard, GCP is its tenet and goal to ensure quality. GCP's methods and measures to ensure the quality of clinical trials mainly include the following:

To specify the qualifications and responsibilities of all relevant personnel in clinical trials;

To stipulate the conditions, procedures and contents of the trial plan for conducting clinical trials;

Specify test records, reports, data processing and archiving systems;

To stipulate management systems for the preparation, distribution, use, and recovery of experimental drugs;

Develop and follow standard operating specifications (SOP) to regulate various tests and operations;

Establish a multi-step quality assurance system;

Contains 4 links: quality control, supervision, inspection and inspection.

(I) Quality Control

PI is fully responsible for quality control, and each researcher or other participating personnel

implements and executes it.

1. Qualifications and responsibilities of test personnel

The investigator is a key factor for the success of clinical trials. Whether it can be completed smoothly and with high quality depends mainly on the investigator. Combined with ICH-GCP, foreign scholars have summarized 12 gold standards for qualified researchers, as follows:

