Familiar with and follow the test plan, read, agree, follow, reach and archive;

Select and train suitable researchers, training, personnel list, resume, and knowing;

Observe and record the test data carefully;

Ensure that the research equipment is adequate and reliable;

Maximum protection of patients;

Accurately predict and record the selection of patients;

Strictly count and manage test drugs;

Record and report adverse events in a timely manner;

Ensure the quality of laboratory evaluation;

Standardize the preservation of test data and files;

Maximize data quality;

Communicate information comprehensively and effectively

This test is a single-center study, and the personnel involved in the test are as follows:

The principal investigator (PI) is the chief researcher;

Sub-investigator (Sub-investigator, SI) participants such as nurses, technicians, etc.;

PI combines the test situation and the center's situation, and arranges qualified personnel to perform related functions.

2. Test plan and implementation of SOP quality assurance

After the trial program is completed, the participating researchers will discuss and revise the program;

After the revised draft is completed, it will be reviewed by the clinical trial committee;

Revise according to the comments of the clinical trial committee to determine the trial plan;

Finalize the test plan and invite statistics and data management personnel to determine;

According to the confirmed test plan, the research database was developed.

(II) Monitor

The purpose of the audit is to protect the rights and interests of patients, the test records and report data are accurate, complete and consistent with the original data, and to ensure compliance with the test plan, standard operating procedures, GCP and current relevant laws and regulations;

The inspector who performs the inspection shall be appointed by the sponsor.

VIII. Patient protection

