This experiment uses an electronic CRF form for manual review and computer inspection; follow the guidelines for filling in the CRF for this test; if there is questionable data after manual review or computer inspection, a data questioning form will be sent to the clinical trial unit and the investigator will sign and confirm the value Correction, data questioning and correction form should be kept.

(II) Statistical Analysis

1. Statistical Analysis Plan

The statistical analysis plan is led by the statistician, assisted by the data administrator, sponsor and researcher, and formulated through consultation. After the trial plan is finalized, statisticians are selected; when about 50% of the enrollment is completed, the statistical analysis plan is started, and the statistical analysis plan is determined when the enrollment of the last case is completed; the statistical analysis plan can be performed before the database is finally locked modify.

2. Sample size

This study is a post-marketing safety observation study, with a design sample size of 600 cases.

3. Statistical analysis sets and statistical methods

Because this trial is a safety monitoring study, the analysis set includes all patients who have used the study drug and have undergone safety evaluation.

The statistical analysis was done using SAS 9.4. This study does not estimate missing data.

All statistical tests are at the 5% level of significance, and the two-sided test may be expressed with a 95% confidence interval.

Describe the basic information of the patient, and use the mean, median, standard deviation, and range for continuous variables for statistical description. Categorical variables (nominal variables/ordinal variables) are described by frequency and frequency.

Calculate the number of adverse events, serious adverse events, adverse reactions and serious adverse reactions, the incidence and its 95% confidence interval, and the 95% confidence interval is calculated using the exact probability method. They are described separately according to the severity of adverse events and whether they are related to drugs.

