Taking adverse reactions and adverse events as dependent variables, taking gender, age, concomitant diseases, gadolinium diamine, gadoteric acid meglumine exposure, combined medication and other factors as independent variables, using Logistic regression to analyze the occurrence of adverse reactions or adverse events. Significant influencing factors, and estimate the odds ratio and its 95% confidence interval. The variables entered into the model will be confirmed in the statistical plan before the data is locked.

X. Trial summary and results publication

After the drug clinical trial summary is completed, at least there should be a statistical analysis report and a clinical trial summary report; after consultation with the investigator, the trial protocol or the results of the analysis after the analysis can be published, and the disclosure of confidential data is strictly prohibited.

The statistical analysis report is completed within one month after the database is locked, and the clinical trial summary report is completed within one month after the statistical analysis report is completed.

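### The serious adverse event definition requires drug causation, so the planned SAE incidence omits serious events judged not drug-caused and largely duplicates the serious adverse reaction line

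*Combined protocol and SAP*

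**What the plan says.** Section VI (IV) 1 gives two definitions in succession. An adverse event is any untoward clinical event during drug treatment, and a causal link is expressly not needed. An SAE is a reaction involving one of six listed outcomes, described as "damages caused by the use of drugs".

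Section IX (II) 3 sets the tabulation: "Calculate the number of adverse events, serious adverse events, adverse reactions and serious adverse reactions, the incidence and its 95% confidence interval", the interval to be exact. It adds: "They are described separately according to the severity of adverse events and whether they are related to drugs". The regression in the same section starts from "Taking adverse reactions and adverse events as dependent variables". It names neither serious adverse events nor serious adverse reactions.

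Causality is rated on six levels (Section VI (IV) 3, and item 16 of the Visit 2–6 form) and rests on the investigator's "clinical judgment and understanding of the trial drug". The form's levels include "Wait to be evaluated". No text says which levels make an event a reaction, and neither adverse reaction nor serious adverse reaction is defined.

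The 24-hour reporting rule stands under a heading about serious adverse events, but its trigger is worded as a reaction: "When an aggregated, serious, or new (not listed in the ACR Contrast Media Guide) adverse reaction occurs".

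**The concern.** The analysis section lists events and reactions separately, both overall and for serious cases, and then splits by relatedness. That layout makes sense only if a serious event can be unrelated to drugs. The SAE definition removes that possibility for any event judged to have no drug cause.

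This is a safety trial with follow-up to 24 months in patients with impaired renal function. Its readers will take an SAE incidence to mean all serious events. Under the written definition it would be a drug-caused figure carrying an all-cause label. Membership would depend on a causality rating with no stated cut-off, and the figure would not be comparable with the background SAE rate that the protocol itself quotes.

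**Working it through.** **1. The definitions against the planned tables**

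| Event | Adverse event line | SAE line (as defined) | Serious adverse reaction line (ordinary meaning) |
|---|---|---|---|
| Serious, judged caused by the contrast agent | yes | yes | yes |
| Serious, judged caused by a concomitant drug | yes | yes | depends on whether a reaction means to the study agent only |
| Serious, judged not caused by any drug | yes | **no** | no |

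The last row appears on neither serious line. The middle row is the only one that can separate the two lines. The first column is complete, so the primary incidence stands.

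**2. Usage elsewhere in the protocol**

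- Section VI (IV) 2 (severity) treats an SAE as one kind of adverse event, with no causal condition.
- Section IV (II) reports 27 SAEs for gadoterate meglumine and says that 2 of them were related. This is all-cause usage; under the definition in Section VI (IV) 1 it would make sense only if the other 25 were caused by other drugs.

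**3. Size, from the background data only**

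Inputs from Section IV (II): n = 2822 patients, 27 SAEs (stated as 1.0%), 2 related (stated as 0.07%). Assumption: one SAE per patient.

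Exact (Clopper–Pearson) limits: lower = Beta⁻¹(0.025; x, n − x + 1), upper = Beta⁻¹(0.975; x + 1, n − x).

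- All-cause: 27/2822 = 0.957%, 95% CI 0.63% to 1.39%. This agrees with the stated 1.0%.
- Related: 2/2822 = 0.071%, 95% CI 0.01% to 0.26%. This agrees with the stated 0.07%.
- Not rated related to the agent: (27 − 2)/27 = 25/27 = 93%.
- Scaled to this trial: 600 × 27/2822 = 5.7 events against 600 × 2/2822 = 0.4.

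The 25 is the most that the written definition would leave out, because some of those events might have been caused by another drug. The data cover one agent and are not described as coming from renal patients or from 24-month follow-up. They illustrate scale and do not predict this trial's rates.

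**4. Whether the all-cause count could be rebuilt later**

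The items listed for Visits 2–6 (Section VI (III)) were checked against the six seriousness criteria.

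- Death has tick boxes, under outcome (item 13) and under impact on the original disease (item 14).
- The other five criteria have no item of their own. They would have to be inferred from the narrative and attachments (item 12) or from partial proxies such as severity, a longer disease course or worsening.
- Severity cannot stand in for seriousness, since Section VI (IV) 2 itself separates the degree of an event from its medical importance.

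One of six criteria is therefore captured directly. Contacts from 3 to 24 months are by telephone (Section II (II)), so details not asked for during the call may be hard to obtain afterwards.

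**The case against.** The strongest reply is that this is a wording slip, possibly from translation. The severity section, the background data and the separate lines in the analysis section all point to the usual all-cause meaning, and staff may well apply that meaning. The SAP can be changed until database lock (Section IX (II) 1), so labels and cut-offs can be settled there. This is fair as to intent. But no current text supplies an all-cause definition, and the only definition given says the opposite. An SAP change also cannot create a seriousness field that the listed form items lack.

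Four stronger readings are tempting, and the documents do not support them.

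- *The two serious lines are one and the same quantity, and the unrelated serious cell must be empty.* The definition says drugs, not the study drug, and the form separates suspected from concomitant drugs (items 7 and 8). Adverse reaction is also undefined. The lines overlap largely, but not provably in full.
- *The comparison of SAEs between agents is biased.* No between-agent SAE test is specified; SAE incidences are reported descriptively and the regression uses other outcomes. A difference in the fraction rated related could also reflect a real difference in drug-caused harm.
- *Serious events judged unrelated will go unreported.* The heading above the triggers refers to serious adverse events, the report form's title covers both events and reactions, and Section VII (I) 1 lists a general duty: "Record and report adverse events in a timely manner". What can be said is that the trigger wording leaves such events unclear.
- *The trial records no seriousness at all.* The fields of the separate report form are not shown. The gap is established only for the listed Visit 2–6 items.

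**Conclusion.** The point holds as an internal inconsistency with a practical consequence. Applied as written, the SAE definition leaves serious events judged not drug-caused out of the SAE incidence, and no other planned line shows all-cause serious events. The primary adverse event incidence is not affected.

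The background data suggest that the difference could be large: up to 25 of 27 SAEs, or 0.96% against 0.07%. That size rests on one agent, another population and one SAE per patient. The conclusion does not depend on it, because it follows from the definitions alone. It does assume that reaction has its ordinary meaning of a drug-caused event and that the written definition is applied. How much could be recovered later depends on the separate report form, whose content is not shown. The definition should be corrected, and the form changed with it.

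**What to change.** 1. In Section VI (IV) 1, define an SAE as any adverse event that meets one of criteria 1–6, regardless of causality.
2. Define adverse reaction, and define a serious adverse reaction as the subset of SAEs at stated relatedness levels. Say whether relatedness means to the study agent or to any drug, and how events still awaiting assessment or not assessable are handled. Fix this before database lock.
3. Add a seriousness item listing criteria 1–6 to the Visit 2–6 adverse event form and the electronic database.
4. Reconcile the adverse reaction wording of the reporting triggers with their heading and with the SAE definition, so that it is clear which trigger, if any, applies to a serious event judged unrelated or not yet assessed. Which rule applies is for the sponsor and the ethics committee.

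Cost: two or three definitions, one form item and the trigger wording, with ethics committee approval of the modification (Section VIII). It is cheapest before the database is built from the confirmed plan (Section VII (I) 2). The downside is more SAE records to process and a seriousness review of any forms already completed. No change to the sample size or the primary analysis is needed.
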